4.2.2 Secondary Outcome Measures

There are also several secondary outcome measures:

- Falls from participant self report, defined as an unexpected event, including a slip or a trip, in which a participant lost their balance and landed on the floor, ground, or lower level, or hit an object like a table or a chair.
- Physical Function measured using the Short Physical Performance Battery assessment
- Frailty phenotype¹⁵, which includes measures of exhaustion, low activity, weight loss, slowed walking, weak grip.
- Alcohol and other drug use from self report measured using the validated Addiction Severity Index (ASI)¹⁶⁻¹⁸
- 5 Study Design

The Boston ARCH 4F Fall Prevention Pilot is a sub-study of the Boston ARCH 4F Study, a longitudinal cohort study of 251 HIV infected men and women who have a spectrum of alcohol and other drug use. The Boston ARCH 4F study aim is to examine the association between alcohol use and falls and fractures and whether frailty mediates these associations in people living with HIV (PLWH). The Fall Prevention Pilot will recruit participants from the Boston ARCH 4F Study to test the acceptability and feasibility of a randomized trial of a 10-week virtual intervention to reduce fall risk PLWH who consume alcohol.

Eligible cohort participants with an elevated risk for falls will be randomized to either the intervention or control (usual care plus educational brochure).

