recording it for research purposes, particularly given the protections in place for such records that is far greater than clinical records, is small. There is a risk that participants may experience loss of confidentiality when research assistants make attempts to contact them for follow-up. All participants will be informed and provide their consent for the study to reach them through contacts they have provided as a part of the Boston ARCH 4F study (the participant will be linked to the Boston ARCH 4F study through their unique Study ID number). When research assistants attempt to make any contact to the participant or other contacts, all communications will be identified as coming from a "health study," not an alcohol abuse or HIV study. When study visits (such as group meetings or individual check-ins) are conducted via phone or confidential video conference, study staff will advise participants to take precautions to minimize the risk of a breach of confidentiality such as participants not to talk about the discussions outside the group, and research study staff will ask all participants not to talk about the discussions outside the group, and not repeat what is said in the group meetings to others. Participants will be asked to only provide their first name or a pseudonym.

How risks will be minimized.

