Loss of confidentiality: To assure confidentiality, research data collection and data entry forms will be labeled only with the unique Boston ARCH 4F Study ID number, and will contain no other individual identification. Only the written informed consent forms, participant locator information, and a master list of participants and participant study identification numbers will have the participant number and identifying information on them. There will be only one master list of names and identification numbers. These data will be kept in a secure electronic environment accessible to the principal investigator, the study research staff and data managers. Study staff will use the tracking information that the participants provided during the Boston ARCH 4F study, and study staff will confirm that the tracking information is up to date and accurate. Computer data will be password protected, and accessible only to research assistants needing the information for follow-up purposes. When study visits (such as group meetings or individual check-ins) are conducted via phone or confidential video conference, study staff will advise participants to take precautions to minimize the risk of breach of confidentiality. Study staff will remind participants that they should participate in study activities in a private location. Participants will be provided the option to keep their camera off, if they would like. Prior to virtual group meetings, we will remind participants that they should not talk about the discussions outside the group. All of these procedures are likely to be effective, based on our experience with similar studies. Comments on the home exercise YouTube videos have been disabled to further protect participant confidentiality.

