6.3 Analysis of Risks in Relation to Benefits

The principal risks of this study are loss of confidentiality and psychological stress. We will take an abundance of caution to protect the confidentiality of participants, and participants will be reminded of best practices prior to each weekly virtual group session. Participants will be provided various opportunities to discuss psychological distress with trained study staff and physician investigators. These risks are outweighed by the potential benefits that participants may receive from the intervention.

Participants who are assigned to the control arm may benefit from the provided educational materials.

Participants who are assigned to the intervention arm may benefit from weekly virtual group sessions and phone check-ins. These sessions will provide participants with the opportunity to discuss challenges

related to falls and alcohol use and ideas for overcoming these challenge. During preliminary qualitative research, Boston ARCH 4F participants expressed that group meetings and individual check-ins would be beneficial. Additionally, the home exercises may improve strength and balance in the participants. Furthermore, this intervention is tailored to address fall risk and alcohol use in this specific population, and it has the potential to reduce falls among PLWH who use alcohol more than a traditional fall prevention program.

The benefits outweigh the risks.

7 Study Subject Selection

- 7.1 Subject Inclusion Criteria
 - Male or female at least 18 years old
 - Prior or current participant in the Boston ARCH 4F Cohort
 - Any alcohol consumption in the last 30 days using Addiction Severity Index
 - Deemed a Fall Risk using the CDC STEADI Fall Risk Assessment Form¹⁹
 - Has reliable access to a phone or computer with internet connection

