Independent Home Exercises: Home based exercises will be tailored to each participant's individual needs and skill sets, which will be determined at the baseline assessment. The general categories of the exercises include air squats, bicep curls, burpees, and single leg stands. Links to the exercises can be found below. Participants will complete assigned exercises on their own at home and will be instructed to record the exercises they complete on the Home Exercise Form, which is a tool for personal use by the participant and will not be returned to the study team. The exercise assignments will take about 30 - 60 minutes to complete per time the participant exercises. During the first virtual group sessions, an occupational therapist member of the study team will describe and demonstrate the assigned exercises. Participants may use this time to ask questions about the exercises. Further, if a participant was unable to attend the first virtual group session, the assigned exercises will be demonstrated by an occupational therapist member of the study team during the first phone check-in. In the case that assigned exercises will be demonstrated at the first phone check-in, the phone check-in will occur using Zoom instead of phone call.

Participants will be able to refer back to video demonstrations of the assigned exercises on a YouTube channel called "Boston ARCH Home Exercises". The YouTube channel will include videos of occupational therapist members of the study team demonstrating the assigned exercises. The videos on the YouTube channel will remain at a visibility status of "unlisted", which means they can only be accessed by a URL. Comments on the videos have been disabled. Study staff will provide participants with the limited access URLs at the first virtual group session, phone check-in, or by email upon participant request. Participants will be encouraged to keep the limited access URLs private and not share the links with people outside of the study.

URLs:

https://youtu.be/BGR69rKSMCA https://youtu.be/mfrOBDuRP7M https://youtu.be/2IeSb2UXsm4 https://youtu.be/3ypbuWluf3M

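### The exercise-video channel carries the parent cohort's name, which is not reconciled with the purpose of the neutral-identification rule in section 6.1

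*Combined protocol and SAP*

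**What the plan says.** Section 8.8 (Independent Home Exercises) lets participants return to demonstrations on "a YouTube channel called 'Boston ARCH Home Exercises". The videos show study therapists. Staff hand out the links at the opening group session, during a check-in call, or by email if the participant asks.

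Section 5 describes the parent study, Boston ARCH 4F, as "a longitudinal cohort study of 251 HIV infected men and women who have a spectrum of alcohol and other drug use".

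Section 6.1, on loss of confidentiality, sets a neutral-identification rule. It opens with "When research assistants attempt to make any contact to the participant or other contacts" and continues that "all communications will be identified as coming from a 'health study,' not an alcohol abuse or HIV study".

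Several safeguards apply to the videos:
- Under section 8.8 they "will remain at a visibility status of 'unlisted', which means they can only be accessed by a URL".
- Section 6.1 adds that "Comments on the home exercise YouTube videos have been disabled to further protect participant confidentiality".
- Section 8.8 also says that "Participants will be encouraged to keep the limited access URLs private and not share the links with people outside of the study".
- Section 6.1 has staff remind participants to take part in study activities somewhere private.

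Section 12.1 allows non-secure messages if the participant has agreed. Their content is then generally kept to a minimum, and participants are advised to delete messages and keep information out of others' sight.

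Section 6.3 states: "The principal risks of this study are loss of confidentiality and psychological stress".

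**The concern.** The rule in 6.1 covers contact with people other than the participant. Its evident purpose is that someone near the participant should not learn from study contact that the study concerns HIV or alcohol. A video channel branded with the cohort's name works against that purpose, because within these documents that name stands for a cohort defined by HIV and substance use.

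The videos are meant for use at home, where other people may see a phone or computer. What is at stake is indirect disclosure of HIV status or alcohol use, which section 6.1 counts among the most sensitive information the study holds. Section 6.1 gives confidentiality as the reason for disabling comments, so the plan already treats the channel as a possible route of disclosure. The name is the one feature of the channel that it leaves unaddressed.

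**Working it through.** The plan gives no figure on this point, so the check is a comparison of text.

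**1. What the name reveals.** It contains the words Boston ARCH. It does not contain HIV, alcohol or the 4F suffix, and the supplied text does not spell out the acronym. The connection to HIV and alcohol comes from section 5. An onlooker would therefore need to know the cohort already or look the name up. Someone who found this protocol could make the connection, since it gives the channel name in 8.8 and describes the cohort in section 5. How likely that is cannot be judged from the documents.

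**2. What the 6.1 rule covers.** Its opening clause ties it to contact attempts by research assistants, and it bars identification as an alcohol or HIV study. It says nothing about the naming of intervention materials, in either direction. An email that delivers a link on request is a communication from staff and so lies close to the rule. A video that the participant chooses to open lies further from it.

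**3. Which safeguard acts on the name.**

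| Safeguard | Section | What it limits | Hides the name on a screen? |
|---|---|---|---|
| Unlisted, reached by link only | 6.1, 8.8 | Who can find the videos | No |
| Comments disabled | 6.1, 8.8 | Traces left by viewers | No |
| Request to keep links private | 8.8 | Onward sharing | No |
| Private-location reminder | 6.1 | Who is nearby | No; it lowers the chance of being seen |
| Minimal detail in non-secure messages | 12.1 | Message content | No; it acts on messages only |

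The private-location reminder follows a sentence about phone and video visits. Whether it extends to exercising alone with a video is not stated.

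**4. What an emailed link shows.** The four links printed in 8.8 are short addresses ending in a string of characters. None contains the cohort's name. The exposure is therefore on the viewing screen, or in a message whose text happens to name the channel. The documents do not give the wording of those messages.

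**5. How often it could arise.** Inputs: about 20 participants randomized to the intervention (section 13), exercises assigned 3 times per week (section 5), and 10 weeks of intervention (section 8.8).

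20 × 3 × 10 = 600 assigned exercise sessions across the arm.

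This counts assigned sessions, not viewings or disclosures. The exercises are demonstrated live at the outset and the videos are optional, so the number of viewings is unknown. So is the share of viewings seen by another person.

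**The case against.** The strongest reply is that no rule is broken. A reader might infer that the protocol contradicts itself, but the text does not support that. The 6.1 sentence governs how research assistants identify themselves when they make contact. It does not say that the health-study label is the only name that may ever appear, and the channel name mentions neither HIV nor alcohol. This part of the objection stands: the point is a tension with the rule's purpose, not a breach of its words.

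A reader might also infer that each viewing, or each emailed link, exposes a participant's HIV status. That is not supported either. The printed links do not carry the name, the videos are described as showing therapists, email is used only on request, and an onlooker would have to recognise or trace the name. Section 6.1 also rates loss of confidentiality as very unlikely, given its procedures. These points stand, and they make the risk small.

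The objection does not dispose of the name itself. As the table shows, the safeguards control access, circulation and surroundings, and none alters what appears on the screen. No section explains why the cohort's name is used or says whether the 6.1 rule reaches the channel.

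**Conclusion.** The point holds as a minor, optional improvement. A channel named after a cohort of people with HIV and alcohol or drug use does not fit the purpose of the neutral-identification rule, and the plan does not reconcile the two. The residual risk is indirect, concerns about 20 people, and has an unknown frequency. The 600 assigned sessions should not be read as a measure of harm.

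The conclusion rests on two assumptions that the documents do not settle: that the channel name is visible when a video is opened, and that some onlookers could connect the name with the cohort. If either fails, the risk largely disappears. The point has no bearing on sample size, outcomes, analysis or the validity of results.

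**What to change.** Three small changes would settle it:
1. Give the channel a neutral name with no cohort reference, for example *Home Exercises*.
2. Use that name in section 8.8.
3. Add a sentence to section 6.1 stating that the neutral-identification rule also covers intervention materials and the messages that carry the links.

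The documents give no video titles, so no specific change to them is asked for; the extended rule would cover them.

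The cost is one rename and two short wording changes, with the IRB approval that section 11 requires for amendments. Data collection and analysis do not change.

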8.9 Individual Check-In via Phone Call

The phone check-in will occur between the first and second weekly virtual group sessions, and follow-up check-ins will occur once weekly after the initial check-in for the entirety of the intervention period, for a total of 10 weekly check-in calls. These phone calls will be conducted with an occupational therapist member of the study team. As the study's primary aim is to assess acceptability and feasibility, there is no set limit of missed weekly check-ins that triggers dropping participant from the study. If a participant stops participating in weekly exercises, the occupational therapist conducting the weekly check in with the participant will inquire as to the reasons why the participant stopped completing the exercises. This feedback will be used to modify the exercises going forward (e.g., frequency, intensity). Additionally, individualized reminders (e.g. phone alarm, calendar update) for the various intervention components will be set during the individual check-ins.

Post-Study Assessment- After the 10 week intervention is complete, all randomized participants (intervention and control groups) will be asked to complete a post-study interview (a series of questionnaires to assess fall history and efficacy, substance use, prescription medications, physical and social environment, food security, and frailty) and physical assessments (physical function measures including grip strength, short physical performance battery, and vision acuity) in-person at BUMC with an RA or RC. Additionally, an occupational therapist member of the research team will conduct the Canadian Occupational Performance Measure. The post-study assessment will take approximately 2 hours to complete. The RAs and RC will reach out to participants approximately 8-9 weeks after randomization to schedule the post-study assessment, and the post-study assessment will be completed approximately 10 weeks (up to 14 weeks) after randomization.

9 Informed Consent

Consent will be sought by trained research staff under the supervision of the study investigators. Research study staff will have a conversation with the potential participant about the study, reviewing all pertinent elements of informed consent. If potential participants wish to review the information and consider their options they may do so and return to enroll at a later date if they remain eligible. Written consent will be documented. Consent will be obtained when potential participants arrive for their first research interview. Their clinical care will not be interrupted or interfered with. Research staff will review the elements of consent with participants (that this is a research study, description of the study procedures including that their study ID will link information from the Fall Prevention Pilot to the Boston ARCH 4F Study, that we will use contact information that was provided for the Boston ARCH 4F study, the risks and discomforts, the benefits, the alternative to participating in the study including to not participate in the research, the purpose and duration of the study, confidentiality, and that participation is voluntary). After research staff review the elements of consent with participants, they will use a "teachback" process among all participants to ensure participant comprehension. The study will begin immediately after informed consent by an RA.

10. Adverse Event Reporting

This study is not greater than minimal risk. Unanticipated Problems, Adverse Events, and protocol deviations will be reported to the IRB as required by IRB policies. The Principal Investigator at BU Medical Campus will report all adverse events and Unanticipated Problems to the IRB in compliance with IRB policy, Federal/State regulations, and sponsor requirements (as applicable).

11. Data Monitoring

The PI will be responsible for ongoing quality control. This includes all aspects of the study related to safety, but also data integrity and protocol compliance. Quality control will include self-audits of data collection and storage as well as compliance with the informed consent procedure. The review of data and procedures may result in early termination of the study, amendment of the protocol or data collection plans, or amendment of study forms. The IRB will be notified and all amendments approved prior to study implementation. In addition, the participants will be notified of any significant new findings that develop during the course of research (e.g., other potential risks) that may affect their wish to continue participation in the study.

The study clinicians, research coordinator, and Principal Investigator will monitor study progress including enrollment, adherence to inclusion/exclusion criteria and study protocol, as well as any adverse events. The Principal Investigator will be responsible for ensuring that adverse events are reported to the local Institutional Review Board in compliance with local and federal requirements. Any changes to the protocol will be made in accordance with local IRB policies. The Principal Investigator will supervise all study activities, including those of the research coordinator and co-investigators, and will be available 24 hours a day by page or telephone.

12. Data Handling and Record Keeping

12.1 Confidentiality

The study ID number assigned to participants in the pilot study will be the same study ID number used in Boston ARCH 4F. This ID number is the only link that connects their identifiers (e.g. names) in the tracking database (information required to contact and follow participants) and the separate study database. This code is stored in a separate secure database accessible only to study staff and investigators.

We will communicate with participants via phone, BU Zoom Meetings for HIPAA, or BU Teams, and when using BMC email, we will type "secure" in the subject line which creates a secure messaging system, or for BU email we will use the BU approved DataMotion SecureMail email service. We note that since technology changes frequently, it is possible that BMC and BU's secure email systems could change and if they do, we will follow BU or BMC IT procedures for such emails. Similarly, if a new secure platform recommended for such communications becomes supported by BU and BMC and/or recommended by the IRB we will use those platforms. One problem that arises with secure email is that it is very difficult for participants to use, particularly the most vulnerable subjects, who have less advanced technology available to them. Thus, if the patient or research subject has agreed, we shall use non-secure communications. In those cases, communication will generally be limited to the minimal detail necessary, and participants will be informed that they should delete messages and take care to keep their information not visible to others on their devices. Please note that this language is based on BU IRB recommendations, and applies to all sections describing participant contact.

Data Management and Security to Protect Privacy: The Biostatistics and Epidemiology Data Analytics Center (BEDAC) will assure high quality forms, monitor data quality, and track and link the multiple data sources. Data will be linked and entered using multiple checks. BEDAC will develop data collection forms and questionnaires, implement procedures for quality control, and provide statistical programming and collaborate in report writing and presentation of study results.

Data will be collected by interview via web-based data capture system on tablets. Study staff in collaboration with BEDAC will design, develop and maintain the electronic data collection forms, and underlying SQL database systems, and implement procedures for data quality control, including multiple checks for entered data. Study staff will use the same secure electronic data capture system that has been successfully implemented in the Boston ARCH 4F study for tracking and contact information. Electronic data collection forms will be designed to read easily, have clear instructions, preprogrammed skip patterns, real-time range checks and internal logic to minimize missing data, resulting in "cleaner" data at capture. The website and accompanying database is located on secure, password-protected servers, behind the Boston University firewalls. The web and database servers use Secure Socket Layering (SSL) to ensure data security and confidentiality. Servers incorporate RAID hard drives for data redundancy. A separate web server dedicated for Cold Fusion applications is also available. Hard copies of the signed informed consent form will be stored in locked filing cabinets and locked offices at Boston University School of Public Health.

Data transmission will be protected through SSL encryption. Eligibility for participants will be verified by the web data capture application. For the pilot trial, allocation is concealed from study staff and participants until the assignment is made to avoid interviewer bias. BEDAC will maintain data management protocols and analytic plans. Study staff will use the Boston ARCH 4F participant tracking system that includes an innovative real-time crosscheck used in prior studies to prompt contact with participants when they appear for care. Because the server is part of the BUMC network, only

connections from users authenticated from the domain controller are accepted, thus providing a secure environment for all data. Specifically, the policies for computer systems security implemented at BUMC are as follows:

Provide physical security of data. The server resides in the same building as the BUMC Office of Information Technology (OIT) servers. The lobby of the building in which the systems reside is under the security purview of the Boston University General Services Security Office and is under surveillance. All central systems are physically secured behind two card-access doors with access to the primary door restricted to key personnel in the OIT. Access through the primary door is also protected by a keypad alarm system that is tied directly into the on-site central emergency response security control center. Written policies exist for contingencies to provide access to the room to those not explicitly authorized.

Provide virtual security via connectivity. Internal access to all systems is done via MicroSoft Challenge Handshake Authentication Protocol. With the exception of internet provider-based services, external client access must first gain access to the internal network before connecting to the systems. This connection is initiated via a Virtual Private Network connection using Pointto-Point Tunneling Protocol or through the University's modem pool which require Kerberos authentication. All web-based mail is encrypted with high-encryption domestic SSL.

All data are protected with disaster recovery via several methods:

Hardware redundancy: Several stages of redundancy exist at the hardware level to minimize failure: Dual-redundant power supplies exist on each disk array; hot-spare disk is configured to automatically self-heal in the event of a disk failure in the array; emergency power generators ensure a 100% electrical uptime; and uninterrupted power supplies present the systems with conditioned steady-state power.

Data backup: Backups are completed daily over the BUMC network using both on-site and offsite disk-based backup devices.

Data Security: All data are stored on servers that are password-protected. To protect against security breaches, data will be electronically encrypted so that only the intended recipient can decode.

BEDAC will use Microsoft SQL Server software for all database development and storage, providing a secure environment for data storage. They will work closely with the BUMC Office of Information Technology (OIT) to secure institutional hardware, software, and network services for data transmission, storage, and archiving to support all URBAN ARCH Consortium research activities.

The BUMC OIT and BEDAC are physically located in the same building; all web and database servers used by BEDAC will be housed in a secure, professionally managed server room under the control of the BUMC OIT. Staff from BEDAC and BUMC OIT work to continually enhance their systems, procedures and processes to ensure compliance with industry and government standards for data security. All central systems are secured physically behind locked doors with access restricted to key personnel in the BUMC OIT. All databases will be backed up automatically on a nightly basis.

13. Statistical Plan

We will enroll up to n=50 participants to accommodate any situation in which an enrolled participant is not randomized to the intervention or control group. We aim to randomize up to n=40 participants

(approximately 20 randomized to the study intervention and approximately 20 randomized to the control group).

The goal of this pilot is to describe feasibility of the proposed trial and intervention and obtain preliminary estimates of falls related outcomes. This pilot is not intended to provide adequate statistical power for a formal comparison of the intervention and control groups on falls-related outcomes.

Confidence intervals for mean number of sessions attended, for those participants randomized to the intervention, will have a width of 0.44 standard deviations, and assuming approximately 80% of the approximately n=40 study participants complete follow-up, a confidence interval for the percent completing the study will have a width of 12 percentage points. While this pilot is not intended to test differences between the intervention and control groups, a t-test comparing means across groups (for example, on frailty scores) requires a large effect (corresponding to a Cohen's d of 1.0) to achieve 80% power, assuming 80% follow-up.

To describe acceptance of the intervention among those randomized to intervention, mean and 95% confidence intervals will be provided for the number of sessions attended and overall satisfaction with the intervention. Compliance with the study protocol will be described the percent and 95% confidence of participants completing the study follow-up evaluation (of all participants). Estimates of intervention effects will be described through odds ratios and 95% confidence intervals for any falls during the intervention period, using logistic regression to control for baseline fall history. Mean differences and 95% confidence intervals for physical function score at the end of the study period, controlling for baseline physical function score, will be estimated through linear regression models.

14. Literature References

